#### **POPULATION PK ANALYSES**

Sparse blood sampling for POPPK analyses will be conducted in all patients initially randomized and treated with CO-1686. A specific population PK data analysis plan will be developed and will outline the detailed approach to data handling, model development and diagnostics, individual model parameter estimation, exploration of covariate effects, and final model evaluation techniques.

#### 11.2.5 Safety Analyses

The safety analyses will be performed using the safety population (all patients who have received at least 1 dose of CO-1686 or erlotinib).

## 11.2.5.1 Extent of Exposure

The following will be summarized by dose group:

- Number of cycles initiated
- Number of dose reductions, delays or interruptions
- Duration of exposure

The number of cycles initiated will be investigated by summarizing the number of cycles started by each patient. The number of patients with at least one dose reduction, delay or interruption will be summarized with frequencies and percentages.

#### 11.2.5.2 Adverse Events

The severity of the toxicities will be graded according to the NCI CTCAE Version 4.03 whenever possible. Treatment-emergent AEs are defined as AEs with an onset date on or after the date of first dose of CO-1686 or erlotinib until the date of the last dose of protocol-specified treatment plus 28 days. AEs will be considered treatment-emergent if all or part of the date of onset of the AE is missing and it cannot be determined if the AE meets the definition for treatment-emergent.

The number and percentage of patients who experienced treatment-emergent AEs for each system organ class and preferred term will be presented by dose group. Multiple instances of the treatment-emergent AEs in each system organ class and multiple occurrences of the same preferred term will be counted only once per patient. The number and percentage of patients with at least one treatment-emergent AE will also be summarized by dose group.

Separate tables will present the following by cohort:

- All treatment-emergent AEs
- Treatment-emergent AEs by CTCAE grade
- Grade 3 or greater treatment-emergent AEs

- Treatment-related, treatment-emergent AEs
- Serious treatment-emergent AEs
- Treatment-emergent AEs with an outcome of death
- Treatment-emergent AEs leading to discontinuation of randomized treatment
- Treatment-emergent AEs resulting in interruption or reduction/delay of randomized treatment

The incidence of treatment-emergent AEs will be summarized by relationship to PO CO-1686 or erlotinib using "treatment-related" and "not treatment-related" categories. If a patient experiences multiple occurrences of the same AE with different relationship categories, the patient will be counted once as a relationship category of treatment-related.

If a patient experiences multiple occurrences of the same AE with different intensity toxicity grades, the patient will be counted once for the maximum (most severe) toxicity grade. AEs with a missing intensity will be presented in the summary table with a toxicity grade of "Missing." For each toxicity grade, the number and percentage of patients with at least 1 treatment-emergent AE of the given grade will be summarized.

Non-treatment-emergent AEs (pretreatment and post-treatment) will be presented in the data listings.

## 11.2.5.3 Clinical Laboratory Evaluations

Clinical laboratory evaluations include the continuous variables for hematology, serum chemistry, and urinalysis. Laboratory values will be presented in International System of Units. The baseline laboratory value will be defined as the last value prior to or on the day of the first dose of CO-1686 or erlotinib, but prior to receiving study drug. The on-treatment period will be defined as the day after the first dose of CO-1686 or erlotinib to 28 days after the last dose of CO-1686 or erlotinib. Laboratory values collected during the on-treatment period will be included in the summary tables. The laboratory values collected after the on-treatment period will only be presented in the data listings.

The summary of laboratory data will include descriptive statistics (N, mean, standard deviation, minimum, median, and maximum) of the maximum, minimum, and last value during the treatment period by dose group and study phase. Summaries using descriptive statistics of the change from baseline to the maximum, minimum, and last value during the on-treatment period will also be given by dose group and study phase. Separate listings will be produced for clinically significant laboratory abnormalities (i.e., those that meet Grade 3 or 4 criteria according to CTCAE) by dose group.

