### Study CO-1686-008

In the patient study (CO-1686-008), PK following HBr salt administration were available from a total of 44 patients (4 started at 500 mg BID, 10 switched from CO-1686 free base to 500 mg BID HBr, 15 started at 625 mg BID, 9 started at 750 mg BID, and 6 started at 1000 mg BID). CO-1686 HBr showed increased absorption and thus, higher exposure than free base. The median  $T_{max}$  was 2 to 3.25 hrs and  $T_{1/2}$  ranged from 1.7 to 4.7 hrs. Following CO-1686 HBr administration, exposure (measured as  $C_{max}$  and  $AUC_{0-24}$ ) increased dose-proportionally from 500 mg to 1000 mg BID (Figure 3-5).

Figure 3-5: Individual CO-1686 AUC0-24 on Day 1 Following 500 mg to 1000 mg CO-1686 HBr BID

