### 5.1.3 End-of-Treatment

All patients should return to the study site for the End-of-Treatment Visit assessments  $28 \ (\pm 7)$  days after the last dose of PO CO-1686 or erlotinib has been administered. In the Phase 2 part only, patients participating in the crossover phase will undergo the End-of-Treatment Visit once, only after discontinuation of crossover CO-1686 treatment. Tumor assessments should be performed at the End-of-Treatment Visit if radiographic disease progression has not been documented previously. An MRI may be used in place of a CT as end-of-treatment scan if required per local authorities.

The treatment phase of the trial will be completed when all enrolled patients have discontinued treatment and completed the End-of-Treatment Visit procedures.

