## 9 STUDY PROCEDURES

Table 9-1 summarizes the procedures and assessments to be performed for all patients.

Table 9-2 summarizes the procedures and assessments to be performed in Phase 2 only for patients randomized to erlotinib, who progress on study, demonstrate T790M+ status at the screening biopsy, and agree to participate in the crossover component of the study to receive PO CO-1686 treatment.

All procedures and assessments are to be completed within  $\pm 1$  day of the scheduled time point and are synchronized with C1D1 of CO-1686 or erlotinib treatment unless otherwise noted.

With the introduction and following approval of this protocol amendment 3 version, crossover to CO-1686 after progression on erlotinib is no longer an option. All ongoing patients, will be treated on the Extension Phase of the study and should follow the schedule of assessments provided in Appendix D.

Table 9-1: Schedule of Assessments in Phase 2 (Before Crossover) and in Phase 3

	Scre	ening			7	Treatment Po		T			Follow-up (Every 8 ± 1 weeks for
Procedure b	≤35 Days Prior to Cycle 1 Day 1	≤ 14 Days Prior to Cycle 1 Day 1	Cycle 1 Day 1 (C1D1) c	Cycle 1 Day 4 ± 1 Day d	Cycle 1 Day 8 ± 1 Day d	Cycle 1 Day 15 ± 1 Day d	Cycle 2 Day 1 (28 ± 3 days after C1D1)	Cycle 2 Day 15 ± 1 Day d	Cycle 3+ Every 28 ± 3 Days	End-of- Treatment t 28 Days ±7 Days After Last Dose	scans, every 3 months ± 7 days for survival and subsequent therapy starting at End-of- Treatment)
Informed consent	X										
Medical/oncology history	X										
Physical examination		X	X				X		X	X	
ECOG performance status		X	X				X		X	X	
Vital signs e , height (screening only) and weight		X	X				X		X	X	
Prior/concomitant medications and procedures f	X		X				X		X	X	
Contraceptive counseling g	X									X	
Serum pregnancy test h		X								X	
Hematology, including reticulocytes i		X	X				X		X	X	
Fasting serum chemistry j		X	X	Fasting glucose only	Fasting glucose only	Fasting glucose only	X	Fasting glucose only	X	X	
Urinalysis k		X									

Table 9-1: Schedule of Assessments in Phase 2 (Before Crossover) and in Phase 3 (Cont.)

	Scre	ening				Treatment P					Follow-up (Every 8 ± 1 weeks for

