#### 11.2.5.4 Vital Sign Measurements

The baseline vital sign measurement will be defined as the last value prior to or on the day of the first dose of CO-1686 or erlotinib. The on-treatment period will be defined as the day after the first dose of CO-1686 or erlotinib to 28 days after the last dose of protocol-specified treatment. Vital sign measurements collected during the on-treatment period will be included in the

summary tables. The vital sign measurements collected after the on-treatment period will only be presented in the data listings.

The summary of vital sign data will include descriptive statistics (N, mean, standard deviation, minimum, median, and maximum) of the maximum, minimum, and last value during the on-treatment period by dose group and study phase. Summaries using descriptive statistics of the change from baseline to the maximum, minimum, and last value during the on-treatment period will also be given by dose group.

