### Table 4. Schedule of Assessments for All Patients

Procedure	Prior to beginning Amendment 3 Evaluations	Day 1 of each cycle	End-of-Treatment Visit (28 ± 7 days after last dose)
Informed Consent	X		
Physical Examination including vision check		X	X
Vital Signs a and Weight		X	X
Concomitant Medications and Procedures		X	X
Contraceptive Counseling b			X
Serum Pregnancy Test c			X
Local hematology including reticulocytes d		X	X
Local fasting Serum Chemistry e		X	X
Adverse events, including SAEs/AESIs f		X	X
CO-1686 dispensing/ administration		X	
Patient diary g		X	X
ECG Assessments using central ECG machine h		X	X
Tumor Scans i	To be done per institution standard of care or 8 ± 1 weeks during treatment; scans are not required at the End of Treatment Visit		
Blood for CYP Evaluation (Optional Sampling)		X j	

a = Vital signs (blood pressure, pulse, and temperature) taken predose on drug administration days.

<sup>b= Patients are to continue using effective contraception for 12 weeks after last dose of CO-1686 or 2 weeks after the last dose of erlotinib and report any pregnancies during this period.

<sup>c = Serum β-hCG to be evaluated by local lab will be performed only on women of childbearing potential.

<sup>d= Includes hemoglobin, hematocrit, WBC and differential (with ANC), platelet count, and reticulocyte count - on Day 1 at each cycle, and at end-of-treatment. Blood will be analyzed by a local laboratory to inform patient treatment decisions, and must be reviewed by the investigator prior to start of CO-1686 or erlotinib administration. Additional tests may be performed at the investigator's discretion.

<sup>e = Includes total protein, albumin, creatinine, BUN or urea, total bilirubin, alkaline phosphatase, ALT, AST, fasting glucose, sodium, potassium, chloride, magnesium, CO2, calcium, phosphorus, total cholesterol, HbA1c - on Day 1 at each cycle, and at end-of-treatment. Samples will be analyzed by a local laboratory. Fast is defined as 8 hour fast (no food or liquid other than water). HbA1c will be measured every other visit (Cycles 3, 5, 7, etc.) after initiating study drug.

<sup>f= Patients will be monitored for AEs/SAEs/AESIs from the time the first dose of CO-1686 or erlotinib is administered through 28 days after the last dose.

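### The last on-treatment laboratory or vital-sign value mixes on-drug and off-drug samples, depending on whether the End-of-Treatment visit falls before or after day 28

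*Combined protocol and SAP*

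**What the plan says.** Section 11.2.5.3 sets the laboratory window: "The on-treatment period will be defined as the day after the first dose of CO-1686 or erlotinib to 28 days after the last dose". Section 11.2.5.4 ends the vital-sign window in the same way, "to 28 days after the last dose of protocol-specified treatment". Later values go to listings only.

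Within the window, laboratory data are summarised as the "maximum, minimum, and last value during the treatment period by dose group and study phase". Changes from baseline to the same three statistics follow. For vital signs, the "change from baseline to the maximum, minimum, and last value during the on-treatment period will also be given by dose group". No by-visit summary is planned for either type of data, although one is planned for patient-reported outcomes (Section 11.2.4.2) and for ECG intervals (Section 11.2.5.5).

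Section 5.1.3 adds: "All patients should return to the study site for the End-of-Treatment Visit assessments". Table 9-1 times that visit at "28 Days ±7 Days After Last Dose", and Appendix D keeps the timing for the Extension Phase: "End-of-Treatment Visit (28 ± 7 days after last dose". Section 9.4 includes hematology, fasting serum chemistry with glucose, and vital signs among the procedures.

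**The concern.** The window closes on day 28 after the last dose, and the End-of-Treatment visit is centred on that same day. The cut-off therefore runs through the middle of the visit window. A patient seen on day 28 contributes an off-drug value under an on-treatment label. A patient seen on day 29 has that value moved to a listing, and the last value reverts to an earlier visit, normally the last cycle visit on drug. One row of the table thus combines two different quantities, and the visit date decides which one a patient contributes.

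This matters because the last value is the only planned laboratory or vital-sign summary that is not an extreme. A reader would naturally take it as the level reached under continued dosing. For an effect that reverses when the drug stops, it shows partial recovery instead. Glucose is the clearest candidate: Section 3.2.1 reports treatment-related hyperglycemia or impaired glucose tolerance in 33.1% of Study CO-1686-008 patients, and Section 7.4.1 warns of possible hypoglycemia once CO-1686 is discontinued.

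Patients still on treatment at data cut-off have no End-of-Treatment value, so the mix could also differ between arms if time on treatment differs. The documents do not allow the size of that difference to be derived.

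**Working it through.** The plan gives no figure for how often the last value is an End-of-Treatment value, so there is nothing to reproduce. The check counts the overlap of the two windows and then varies what the documents leave open.

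**Inputs from the documents.** On-treatment cut-off: day 28 after the last dose (Sections 11.2.5.3 and 11.2.5.4). Visit window: 28 − 7 = day 21 to 28 + 7 = day 35, which is 15 days (Table 9-1).

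**Inputs assumed.** Visit timing within the window, attendance, and full reversal of the effect by day 21. The documents give none of these.

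**Overlap.** Days 21 to 28 inclusive are 8 days inside the on-treatment period. Days 29 to 35 are 7 days outside it.

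**Share of discontinued patients whose last value is off drug.** Share = attendance × (weight on days 21–28 ÷ weight on days 21–35).

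**Retained change.** If the on-drug change is D and reversal is complete, the mean change to last value is (1 − share) × D.

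| Assumed timing | Weight on days 21–28 ÷ total | Share, all attend | Share, 80% attend | Retained, all attend | Retained, 80% attend |
|---|---|---|---|---|---|
| Uniform | 8/15 | 53% | 43% | 47% | 57% |
| Triangular around day 28 | 36/64 | 56% | 45% | 44% | 55% |
| Half exactly on day 28, rest uniform | 147/196 | 75% | 60% | 25% | 40% |
| Early-skewed (weights 15 down to 1) | 92/120 | 77% | 61% | 23% | 39% |
| Late-skewed (weights 1 up to 15) | 36/120 | 30% | 24% | 70% | 76% |

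The share runs from 24% (late-skewed, 80% attendance) to 77% (early-skewed, all attend). The retained part of a fully reversible change runs from 23% to 76%. Incomplete reversal would raise the retained part.

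**Scope.** Urinalysis is done at screening only (Section 9.6.1.2), so it is unaffected. HbA1c is in the chemistry panel but is a slow marker and need not reverse in three to four weeks.

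**After the fix.** If the last value must be taken before day 21, none of the 15 visit days can supply it, and the End-of-Treatment dilution in the last-value row is removed.

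**The case against.** The strongest reply is that the safety analysis as a whole loses little. Section 11.2.5.3 also summarises the maximum and the change to the maximum, and it lists Grade 3/4 laboratory abnormalities. Section 11.2.5.2 tabulates treatment-emergent adverse events by grade and by effect on dosing. Section 10.5 records an abnormal laboratory value as an adverse event when it needs intervention. The 28-day window also matches the adverse event window. All of this stands, and it confines the point to one of three statistics.

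A reader might infer more, in three ways that the documents do not support:

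- **That the last value is usually the End-of-Treatment value.** Neither visit timing nor attendance is given, and Section 12.1 asks for end-of-treatment procedures only as far as possible. Patients still on treatment at data cut-off have no such visit. Phase 2 crossover patients have one only after crossover CO-1686 (Section 5.1.3). Several of the assumed shares fall below half.
- **That raised glucose disappears from the report.** The other outputs listed above keep it visible.
- **That the CO-1686 half-life, which "ranged from 1.7 to 4.7 hrs", proves recovery.** Day 21 is 21 × 24 ÷ 4.7 = 107 or more parent half-lives after the last dose. However, Section 7.4.1 attributes hyperglycemia to a metabolite whose half-life is not stated, and CO-1686 is described as an irreversible inhibitor. Parent half-life therefore does not measure the offset of the effect.

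Two further cautions stand. No section states what the last value is meant to show. On-drug glucose may also already be lowered by anti-hyperglycemic treatment, so the last value is a modest signal even when it is taken on drug. Neither makes an off-drug sample an on-treatment one.

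**Conclusion.** The point holds in a limited form. As written, End-of-Treatment chemistry, hematology and vital-sign values from days 21 to 28 enter the last-value and change-to-last summaries as on-treatment data, while those from days 29 to 35 do not. No other section repairs this.

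For effects that reverse off drug, the last-value summary is diluted. Under uniform timing, full attendance and full reversal, 53% of discontinued patients contribute an off-drug value and 47% of the on-drug change remains. Across the assumptions tried, the share is about 24% to 77%. The overlap of 8 days in 15 is fixed by the plan; the rest is assumption.

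The severity is minor: the summaries are descriptive, and no test, endpoint or decision rule depends on them. It is a cheap improvement, still worth making because Section 13.9 plans a clinical study report.

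**What to change.** In Sections 11.2.5.3 and 11.2.5.4:

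1. Define the last on-treatment value as the last sample taken up to the last dose, or within a short pre-specified number of days after it that ends before day 21. The allowance keeps samples drawn just after dosing stops for toxicity, which a strict cut-off at the last dose would discard.
2. Report the End-of-Treatment value and its change from baseline as a separate post-treatment row, using all visits on days 21 to 35. Amend the listings-only rule so that visits on days 29 to 35 enter this row.
3. Keep the 28-day window for adverse events and for maximum and minimum values.
4. Use one defined term. Section 11.2.5.3 refers to the treatment period for raw values and to the on-treatment period for changes, and defines only the latter.

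The cost is wording and one extra table row, with data already collected. There are two drawbacks. One table then carries two windows and needs a footnote. For some patients the last on-drug value will be up to about one cycle old, since scheduled chemistry is every 28 ± 3 days after Cycle 2. The present rule already accepts this for patients seen on days 29 to 35.

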# 4.1.2 Secondary Objectives

- To compare secondary measures of clinical efficacy (ORR, DR, and OS) of oral single-agent CO-1686 with that of erlotinib when administered as a first-line targeted treatment in patients with advanced/metastatic NSCLC whose tumors have EGFR-activating mutations
- To assess PFS, ORR, DR, and OS in patients with baseline T790M mutations based on central allele-specific polymerase chain reaction (PCR) EGFR mutation assay
- To assess quality of life (QOL) using the patient-reported outcomes (PRO) of European Organization for Research and Treatment of Cancer Core Quality of Life Questionnaire (EORTC QLQ-C30) and the EORTC Quality of Life Questionnaire Lung Cancer module (EORTC QLQ-LC13), 15 the Dermatology Life Quality Index (DLQI), 16 and the EQ-5D instrument 17 in patients receiving treatment with CO-1686 versus erlotinib
- To evaluate safety and tolerability of CO-1686 versus erlotinib in patients with advanced/metastatic NSCLC whose tumors have EGFR-activating mutations
- To determine PK of CO-1686 in this patient population using population PK (POPPK) methods and explore correlations between PK, exposure, response, and/or safety findings

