# Management of Hyperglycemia

CO-1686 causes hyperglycemia in some patients secondary to inhibition of the insulin-like growth factor 1 receptor (IGF-1R) and insulin receptor (IR) kinases by a metabolite. Therefore, some patients will require addition of a glucose lowering medication and patients with pre-existing diabetes may require more frequent monitoring and/or adjustments of diabetic medication. Clinical experience with CO-1686 suggests hyperglycemia generally occurs within the first 3 weeks of treatment, leading to the need for more intensive glucose monitoring during the first several weeks of the study. In Phase 1/2 clinical trial experience, increased nausea, vomiting, decreased appetite, diarrhea, muscle cramps and fatigue have been reported in patients with hyperglycemia. Such patients must be closely monitored including assessment of fasting glucose levels and early initiation of anti-hyperglycemic therapy. As CO-1686-induced hyperglycemia is mediated through insulin resistance, agents that suppress glucose synthesis (metformin), increase sensitivity to insulin (glitazones) or increase glucose excretion (sodium- glucose cotransporter 2 [SGLT2] inhibitors) are expected to be more effective than those that increase plasma insulin (sulphonylureas or exogenous insulin). Metformin has been used most frequently in CO-1686 clinical studies and is, therefore, recommended as the initial agent to manage hyperglycemia in patients with normal renal function. In addition, preliminary data from the ongoing Study CO-1686-008 suggest that starting metformin at the same time CO-1686 therapy is initiated may prevent development of CO-1686-induced hyperglycemia. For all patients, irrespective of whether they are receiving metformin prophylactically or therapeutically, glucose monitoring should be conducted according to the following schedule:

Fasting glucose will be measured at the following visits: screening, C1D1, C1D4 (± 1 day), C1D8 (± 1 day), C1D15 (± 1 day), C2D1, C2D15 (± 1 day), C3D1, C4D1, C5D1, CND1 and End-of-Treatment Visit.

The following guidelines for management of hyperglycemia are based on experience in the Phase 1 study. Whilst the blood glucose thresholds for intervention outlined below should be followed, management of individual patients should be based on local practices and the treating physician's

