Abbreviations: AAG = alpha-1 acid glycoprotein; ALT = alanine aminotransferase; ANC = absolute neutrophil count; AST = aspartate aminotransferase; β-hCG = beta human chorionic gonadotropin; BUN = blood urea nitrogen; CT = computed tomography; ECG = electrocardiogram; ECOG = Eastern Cooperative Oncology Group; EGFR = epidermal growth factor receptor; EORTC QLQ-C30 = European Organization for the Research and Treatment of Cancer Quality of Life Questionnaire, Core 30; EORTC QLQ-LC13 = European Organization for the Research and Treatment of Cancer Quality of Life Questionnaire, Lung Cancer 13; MRI = magnetic resonance imaging; RECIST = Response Evaluation Criteria in Solid Tumors; WBC = white blood cells

- a CO-1686 will be administered PO at 500 mg BID, with a meal or within 30 minutes after a meal and erlotinib will be administered PO QD at 150 mg on an empty stomach (1 hour before or 2 hours after ingesting food)
- b Unless specified, procedure is completed ± 1 day of scheduled time point and is synchronized with C1D1 of CO-1686 or erlotinib.
- c C1D1 and randomization can be the same day, but not required. C1D1 must be within 3 days of randomization. Procedures required on C1D1 may be omitted if completed ≤ 3 days earlier during the screening period.
- Fasting glucose required on  $C1D4 \pm 1$  day,  $C1D8 \pm 1$  day,  $C1D15 \pm 1$  day, and  $C2D15 \pm 1$  day for patients taking CO-1686 only. Not required for patients taking erlotinib.
- Vital signs (blood pressure, pulse, and temperature) taken predose on C1D1 and without reference to dose at every subsequent visit. All vital signs will be obtained after the patient has been resting for at least 5 min. Height is only required once at screening. Weight is measured at each visit.
- f On C1D1 concomitant medications and procedures will be monitored pre- and postdose.
- g Patients are to continue using double-barrier contraception for 12 weeks after last dose of CO-1686 and 2 weeks after the last dose of erlotinib and report any pregnancies during this period.
- h Serum β-hCG (evaluated by local labs) will be performed only on women of childbearing potential ≤ 3 days prior to C1D1 and at end-of-treatment. If the serum pregnancy test results are not available on Day 1, a urine pregnancy test can be performed on C1D1 to confirm that the patient is not pregnant prior to dosing.

Table 9-1: Schedule of Assessments in Phase 2 (Before Crossover) and in Phase 3 (Cont.)

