	Scre	ening			Т	reatment Policy (Daily Dosing					Follow-up (Every 8 ±
Procedure b	≤35 Days Prior to Cycle 1 Day 1	≤14 Days Prior to Cycle 1 Day 1	Cycle 1 Day 1 (C1D1) c	Cycle 1 Day 4 ± 1 Day d	Cycle 1 Day 8 ± 1 Day d	Cycle 1 Day 15 ± 1 Day d	Cycle 2 Day 1 (28 ± 3 days after C1 D1)	Cycle 2 Day 15 ± 1 Day d	Cycle 3 + Every 28 ± 3 Days	End-of- Treatment t 28 Days ±7 Days After Last Dose	1 weeks for scans, every 3 months ± 7 days for survival and subsequent therapy starting at End-of-Treatment)

- i Includes hemoglobin, hematocrit, WBC and differential (with ANC), platelet count, and reticulocyte count ≤ 14 days prior to the first day of dosing (C1D1), on Day 1 for all subsequent cycles, and at end-of-treatment. Blood will be analyzed by a local laboratory to inform patient treatment decisions, and must be reviewed by the investigator prior to start of CO-1686 or erlotinib administration. Additional tests may be performed at the investigator's discretion.
- Includes total protein, albumin, creatinine, BUN or urea, total bilirubin, alkaline phosphatase, ALT, AST, fasting glucose, sodium, potassium, chloride, magnesium, CO2, calcium, phosphorus, total cholesterol, HbA1c ≤ 14 days prior to first day of dosing (C1D1), on Day 1 for all subsequent cycles, and at end-of-treatment. Samples will be analyzed by a local laboratory. Fast is defined as 8 hour fast (no food or liquid other than water). HbA1c will be measured every other visit (Cycles 3, 5, 7, etc.) after initiating study drug. Fasting glucose at C1D4, C1D8, C1D15, and C2D15 is only required for patients randomized to CO-1686.
- k Includes dipstick for protein, glucose, blood, pH, and ketones ≤ 14 days prior to first day of dosing (C1D1). Samples will be analyzed by a local laboratory. If dipstick findings are abnormal, then a microscopic evaluation will be performed to assess the abnormal findings.

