## 9.6.1.2 Clinical Laboratory Investigations

Blood will be analyzed by a local laboratory to inform patient treatment decisions and must be reviewed by the investigator prior to start of CO-1686 or erlotinib administration. Additional tests may be performed at the investigators discretion. The panels of laboratory tests to be performed are shown below.

**Hematology:** Hemoglobin, hematocrit, WBC and differential (with ANC), reticulocyte count, and platelet count per the schedule of evaluation at screening, during treatment, and at the

End-of-Treatment Visit. Hematology results must be reviewed by the investigator prior to the start of treatment with CO-1686 or erlotinib.

Patients known to require concomitant therapy with anticoagulant therapy such as warfarin (Coumadin®) should have international normalized ratio (INR) monitored at screening and during the study.

**Fasting glucose- for all patients taking CO-1686**: must be measured following an 8 hour fast (no food or liquid other than water) at screening, C1D1, C1D4, C1D8, C1D15, C2D1, C2D15, and every Cycle *N* D1 thereafter and at End-of-Treatment Visit, also if clinically indicated on study. Fasting glucose is measured as part of clinical chemistry panel (see below) on all cycles Day 1 visits, and measured individually C1D4, C1D8, C1D15, and C2D15.

In the Phase 2 part only: For crossover patients, fasting glucose will be measured at XO-screening, XO-C1D1, XO-C1D4, XO-C1D8, XO-C1D15, XO-C2D1, XO-C2D15 and every Cycle XO-N D1 thereafter and at End-of-Treatment Visit, also if clinically indicated on study. Fasting glucose is measured as part of clinical chemistry panel (see below) on all XO-cycles Day 1 visits, and measured individually on XO-C1D4, XO-C1D8, XO-C1D15, and XO-C2D15.

**Clinical chemistry:** Total protein, albumin, creatinine, BUN or urea, total bilirubin, alkaline phosphatase, ALT, AST, total cholesterol, HbA1c, *fasting* glucose, sodium, potassium, chloride, CO2 (or bicarbonate), calcium, magnesium, and phosphorus per the schedule of evaluations at screening, during treatment, and at the End-of-Treatment Visit. Serum levels of AAG will be determined on PK sampling days. HbA1c will be measured at screening and every other cycle (Cycle 3, 5, 7, etc.) while the patient is on study.

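### Fasting glucose is drawn four extra times in the CO-1686 arm only, so the planned per-patient maximum and minimum differ slightly between arms through sampling alone; add a common-visit summary

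*Combined protocol and SAP*

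**What the plan says.** **Sampling.** In Section 9, Table 9-1 footnote j states: "Fasting glucose at C1D4, C1D8, C1D15, and C2D15 is only required for patients randomized to CO-1686". Footnote d, on the same four visits, says: "Not required for patients taking erlotinib". Section 9.6.1.2 gives the CO-1686 schedule: fasting glucose "must be measured following an 8 hour fast (no food or liquid other than water) at screening, C1D1, C1D4, C1D8, C1D15, C2D1, C2D15", then Day 1 of every later cycle and End-of-Treatment, and when clinically indicated. Both arms have fasting chemistry, including glucose, at screening, Day 1 of each cycle and End-of-Treatment.

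**Analysis.** Section 11.2.5.3 states: "Laboratory values collected during the on-treatment period will be included in the summary tables". It then plans descriptive statistics "of the maximum, minimum, and last value during the treatment period by dose group and study phase", and the "change from baseline to the maximum, minimum, and last value during the on-treatment period will also be given by dose group and study phase". I read dose group as treatment arm. The section does not limit the tables to visits common to both arms, and it makes no allowance for the number of samples.

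**Purpose.** Section 4.1.2 includes a comparative safety objective: "To evaluate safety and tolerability of CO-1686 versus erlotinib in patients". Section 4.2.2 lists laboratory abnormalities among the secondary endpoints.

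**The concern.** A maximum or minimum depends on how many values it is taken from. Take two patients with identical glucose behaviour, one sampled four more times than the other. On average the first will show a higher maximum and a lower minimum. Here the extra draws all fall in one arm, and they concern the analyte most relevant to that drug's toxicity.

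Timing adds to the imbalance. The hyperglycemia guidance in Section 7.4.1 says that "hyperglycemia generally occurs within the first 3 weeks of treatment". In that window a CO-1686 patient has three scheduled post-dose glucose values (C1D4, C1D8, C1D15) and an erlotinib patient has none. The all-values contrast therefore mixes three things: a drug effect seen at visits both arms attend, an early drug effect looked for in one arm only, and a pure count effect. At stake is the stated size of the glucose difference in the comparative laboratory tables. The monitoring schedule itself is not in question.

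**Working it through.** The plan gives no figure for this comparison, so there is none to reproduce. The check asks how far the planned extremes would differ if CO-1686 had no effect on glucose.

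**Step 1: scheduled on-treatment values.** C1D1 is baseline. Count Day 1 visits from Cycle 2 onward (28-day cycles), plus End-of-Treatment, plus four for CO-1686. A month is 30.4375 days. At 2 months, for example, an erlotinib patient has C2D1, C3D1 and End-of-Treatment (3 values), and a CO-1686 patient has 3 + 4 = 7.

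**Step 2: expected maximum.** For n independent standard normal values, E(max) = ∫ x · n · φ(x) · Φ(x)^(n−1) dx. Units are within-patient SD, because the documents give no glucose SD. By symmetry the minimum moves down by the same amount. Each patient has one baseline value in either arm, so the change from baseline to each extreme shifts equally.

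| Months on treatment | Erlotinib n | CO-1686 n | E(max), erlotinib | E(max), CO-1686 | Shift (SD) |
|---|---|---|---|---|---|
| 2 | 3 | 7 | 0.846 | 1.352 | 0.51 |
| 6 | 7 | 11 | 1.352 | 1.586 | 0.23 |
| 10 | 11 | 15 | 1.586 | 1.736 | 0.15 |
| 13 | 15 | 19 | 1.736 | 1.844 | 0.11 |

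**Step 3: average over exposure.** I simulated 100,000 patients per arm with no drug effect. Exposure was exponential with a 10-month median in both arms, using the erlotinib PFS assumption in Section 11.3 as a stand-in. Each extra draw was counted only if the patient was still on treatment at that day. The mean difference, CO-1686 minus erlotinib, was +0.23 SD for the maximum and −0.23 SD for the minimum.

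**Step 4: in mg/dL.** For an assumed within-patient SD of 10 to 30 mg/dL: 0.233 × 10 = 2.3 and 0.233 × 30 = 7.0, so about 2 to 7 mg/dL.

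**Step 5: serial correlation.** If a patient's deviations share a common correlation ρ, the shift is multiplied by √(1 − ρ). With an assumed ρ of 0.5 the average becomes 0.233 × 0.707 = 0.16 SD.

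**Step 6: unequal exposure.** With medians of 13 months (CO-1686) and 10 months (erlotinib), the PFS assumptions in Section 11.3, the maximum shifts by +0.32 SD with the extra draws and +0.12 SD without them.

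**Step 7: effect of the fix.** Restricting both arms to shared visits at equal exposure brings the simulated difference to 0.00 SD for the maximum and for the minimum.

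**The case against.** The case for leaving the section alone has real substance.

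- **The tables are descriptive.** Section 11.2.5.3 names no glucose test and no decision rests on one; Section 11.2.1 gives only a general t-test for means. This stands, and it keeps the point minor. The tables will still be read across arms, because the objective is comparative.
- **Balanced measures exist.** The last value does not depend on the number of draws, and HbA1c is scheduled every other cycle in both arms. This also stands, but neither corrects the maximum and minimum.
- **A common-visit table alone would mislead the other way.** The first shared post-dose visit is C2D1, about day 28, after the period when hyperglycemia usually appears and after glucose-lowering treatment may have begun. A reader might infer that the planned table should be replaced. The documents do not support that, since it would take the early peaks out of the two-arm display.
- **Little is left to collect.** Development has stopped, no more patients will be enrolled, and the Appendix D schedule has no arm-specific glucose draws. Only Cycle 1 and 2 data already collected are affected. However, Section 13.9 still calls for a clinical study report, and the fix needs no new data.

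Two stronger readings are tempting. One is that the hyperglycemia excess is itself a sampling artefact. Against that, Table 3-2 reports treatment-related hyperglycemia in 11 of 18 patients (61.1%) at 500 mg BID, and Appendix D Table 1 reports Grade 3 or greater hyperglycemia in 17% to 44% by acetylator status. A few mg/dL in a mean maximum does not produce those rates. The other is that CO-1686 would show several times as many patients above a mild glucose threshold early in treatment. Section 11.2.5.3 plans no threshold table and no early-window table, and any such figure needs a glucose mean and SD that the documents do not give.

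**Conclusion.** The point holds as a small, avoidable distortion. As written, the glucose maximum and minimum, and the change to each, depend partly on how often each arm was sampled. At equal exposure, with no drug effect and independent values, the artefact is about 0.1 to 0.5 within-patient SD depending on time on treatment, and about 0.23 SD on average. It is largest for patients who stop early. The mg/dL range rests on an assumed SD, and positive serial correlation shrinks it.

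The effect widens both extremes, so a one-directional bias against CO-1686 describes only the maximum. The Grade 3 or 4 laboratory listings share the same unequal ascertainment. Part of any observed difference will be real drug effect, and the count artefact does not call the severe hyperglycemia signal into question.

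**What to change.** In Section 11.2.5.3:

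1. Keep the planned glucose summary of all on-treatment values. Add a label saying that CO-1686 patients had four additional scheduled draws (C1D4, C1D8, C1D15, C2D15).
2. Add a between-arm glucose summary of the maximum, the minimum and the change from baseline to each, restricted to visits scheduled in both arms: Day 1 of Cycle 2 onward and End-of-Treatment. State that this table is the one to use for the size of the arm difference.

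The cost is one extra table from data already held; the assessment schedule does not change. The common-visit table will miss early CO-1686 peaks, so the two tables should be shown together. It will not remove differences due to unequal time on treatment (about 0.12 SD at 13 against 10 months), and a table note should say so.
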